9.1.5 Duration of Response

Duration of Overall Response: The duration of overall response is measured from the time measurement criteria are met for CR or PR (whichever is first recorded) until the first date that recurrent or PD is objectively documented (taking as reference for PD the smallest measurements recorded since the treatment started).

The duration of overall CR is measured from the time measurement criteria are first met for CR until the first date that PD is objectively documented.

Duration of Stable Disease: Stable disease is measured from the start of the treatment until the criteria for progression are met, taking as reference the smallest measurements recorded since the treatment started, including the baseline measurements.

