- \geq 25% increase in the sum of perpendicular diameters of the indicator lesions, OR
- \geq 25% increase in the total lesion count, or a minimum of five new lesions, whichever is greater, OR
- ≥ 25% increase in the number of raised lesions (minimum of five new raised lesions if there are very few raised lesions, for example ≤ 8), whichever is greater.

Note: There are body sites where disease is particularly difficult to evaluate, and a few new lesions may be counted in spite of the fact that a participant is not actually progressing. For example, lesions of the foot, particularly those which are flat, are difficult to evaluate because their intensity may be variable based on how much edema is present, how much the person walked the day before, how long their feet have been in a dependent position prior to the physical exam, etc.

For participants with >50 cutaneous lesions

• 25% increase in the sum of the perpendicular diameters of the indicator lesions, OR

- 25% increase in the total number of lesions in the prospectively defined anatomic sites containing representative numbers of lesions, OR
- A total of five new lesions in anatomic sites which were previously documented as having no evidence of cutaneous disease on the whole-body diagram, OR
- 25% increase in the number of raised lesions (minimum of five raised lesions if there are very few raised lesions, for example <8) whichever is greater. Photographic documentation of "gross" or significant progression, particularly in areas that were not being followed, will be of particular value.

In order to classify a response as PR, the participant must have at least a PR in either the cutaneous or noncutaneous sites of disease, and no evidence of progression as defined in the above criteria. In order to classify a response as a CR, the participant must have a CR in both the cutaneous (if applicable) and noncutaneous (if applicable) sites of disease and no evidence of progression as defined by the above criteria.

Noncutaneous Progression

Progressive disease includes new visceral sites of involvement or progression of visceral disease or the development of new or increasing tumor-associated edema or effusion lasting at least 1 week, which interferes with the participant's normal activities. Progressive visceral disease, for measurable and evaluable disease, should be analogous to non-KS response criteria (RECIST; see Section 9.1).

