- 9.2.5 Recurrent disease is defined as the appearance of tumor following documentation of a complete remission.
- 9.2.6 Time to response is defined as time from the first dose of chemotherapy until documentation of first response.
- 9.2.7 Time to progression is defined as time from initiation of chemotherapy to documentation of first progression.
- 9.2.8 Response duration is defined as the time from first documentation of response to documentation of first progression.

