10.4 Analysis of Secondary Endpoints

10.4.1 Preliminary objective response rates

The proportion of participants achieving ORs (by RECIST criteria or KS response criteria, which includes RECIST for visceral disease, or by RECIL for cHL) and their corresponding 95% confidence intervals (calculated using exact Binomial) will be reported separately for solid tumor and cHL according to treatment (combination therapy and single agent) using response criteria designated in Section 9.0. Participants in the expansion cohort and those treated at any Dose Level in the dose de-escalation cohorts will be included. Disease-specific outcomes will be estimated for histologies with > 5 participants. For participants who fail therapy, the proportion with loco-regional vs. distant progression will be summarized. Descriptive statistics will also be compiled for DOR.

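### The Kaposi sarcoma response-duration rule in 9.2.8 ends only at progression and omits recurrence, so a relapse from CR with one to four non-indicator skin lesions does not end the response

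*Combined protocol and SAP*

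**What the plan says.** Three parts of the protocol decide when a KS response ends.

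- **Duration (9.2.8):** "Response duration is defined as the time from first documentation of response to documentation of first progression". Progression is the only end event named.
- **Recurrence (9.2.5):** "Recurrent disease is defined as the appearance of tumor following documentation of a complete remission". No minimum number of lesions is attached, and neither 9.2.7 nor 9.2.8 refers to this category.
- **Progression (9.2.4, 50 or fewer cutaneous lesions):** a 25% "increase in the total lesion count, or a minimum of five new lesions, whichever is greater"; or a 25% "increase in the sum of perpendicular diameters of the indicator lesions"; or a 25% rise in raised lesions, with a minimum of five when few are raised. New or worsening visceral disease, and edema or effusion that meets the stated conditions, also count. The cutaneous rules do not say whether the increase is measured from baseline or from the smallest value on study.

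Under 9.2.3, a status that is not CR, PR or PD is stable disease.

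For tumors assessed by RECIST, Section 9.1.5 runs duration "until the first date that recurrent or PD is objectively documented", with the smallest measurements since treatment start as the reference for PD. For the Hodgkin cohort, 9.3.10 is worded like 9.2.8, but 9.3.6 places relapse after CR under one heading with PD.

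Section 10.4.1 puts DOR to use: "Descriptive statistics will also be compiled for DOR".

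**The concern.** Duration of response is meant to stop when the response is lost. In the KS section, the protocol defines the loss of a complete remission and then leaves it out of the rule that times the response. The threshold that remains is five new lesions on count, so tumor can be documented as having returned while the participant still counts as in response.

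KS is one of the three histologies named in secondary objective 1.2.2 and one of the three tumor types admitted to the combination expansion cohort. Section 10.4.1 takes solid tumors as one group, scored by RECIST or by the KS criteria. A DOR summary for that group would then combine participants whose response ends at recurrence with participants whose response does not.

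**Working it through.** The documents give no DOR figure, so there is nothing to reproduce. The check applies the written rules to possible courses.

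**1. Relapse after CR, 50 or fewer lesions.** The count rule is: PD if (current count − reference) ≥ max(25% of reference, 5).

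- *Reference is the nadir, 0 lesions after CR.* The threshold is max(0, 5) = 5. One, two, three or four returning lesions are not PD; five are.
- *Reference is baseline.* With 5, 10, 20 or 40 baseline lesions, count-PD is reached only at 10, 15, 25 or 50 lesions.

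Example: 12 lesions, then CR, then three skin lesions. From nadir the rise is 3, below 5. From baseline the threshold is 12 + max(3, 5) = 17. Neither is PD, yet 9.2.5 calls the course recurrent disease. The raised-lesion rule behaves the same way, because its minimum of five applies when few lesions are raised.

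This result therefore does not depend on which reference is meant. It does depend on two conditions: the returning lesions lie outside the indicator set, and there is no new visceral site or qualifying edema. If an indicator lesion reappears and the reference is its nadir of zero, the percentage rise is undefined and could be read as PD.

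**2. Same course under the other rules.** Under 9.1.5, recurrence ends the response, and under 9.1.4.1 one new lesion is progression. Under 9.3.6, relapse after CR sits with PD. Only the KS rule leaves the response open.

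**3. Possible delay (illustration; growth rates are assumptions).** KS is assessed every 4 weeks (9.2). With g new lesions per visit and a nadir of zero, the fifth lesion is reached at visit ceil(5/g), counting from the visit at which recurrence is first seen. Delay = 4 × (ceil(5/g) − 1) weeks.

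| New lesions per visit | Visits to five | Delay (weeks) |
|---|---|---|
| 1 | 5 | 16 |
| 2 | 3 | 8 |
| 3 or 4 | 2 | 4 |
| 5 or more | 1 | 0 |

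**4. Regrowth after PR.** Take a 50% fall in the indicator-lesion products, then a return to baseline.

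- *From baseline:* the change is 0%, so it is not PD on size. The same holds for count and raised lesions.
- *From nadir:* products rise by 1/0.5 − 1 = 100%. With uniform change, diameters rise by 1/√0.5 − 1 = 41%, above 25%, so it is PD.

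The answer turns on a reference that 9.2.4 does not state. Under a nadir reading, the minimum of five leaves a small remainder. With a reduction of about 50%, return to baseline misses the count rule at 5 to 8 baseline lesions (a returning indicator lesion may still trigger the size rule). It misses the raised-lesion rule at 2 to 8 baseline raised lesions.

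**The case against.** **The five-lesion minimum is deliberate.** Section 9.2.4 warns that a few lesions, especially flat ones on the foot, may be counted when a participant is not progressing. That explains the threshold for PD. It does not explain why 9.2.8 passes over 9.2.5, which concerns tumor appearing after documented complete remission and carries no threshold.

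**Other text may fill the gap.** KS is a solid tumor, so 9.1.5 might be thought to cover it; but 9.2.8 is the specific KS rule, and 9.2.4 sends the reader to RECIST only for visceral disease. Section 9.2 also refers to a KS Tumor Assessment manual that is not among the documents and might state the reference value. This stands as a limit on the baseline-or-nadir point.

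**Stronger readings.** A reader might infer that responses are also overstated after PR. That does not follow, because it needs a baseline reference that 9.2.4 does not state. A reader might infer that KS DOR always errs toward longer than RECIST DOR. It need not: KS progression has triggers of its own, such as edema and the raised-lesion count, which can end a response without a 20% size increase. A reader might also put one figure in weeks on the overstatement, but any such figure rests on an assumed growth rate.

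**The consequence is small.** DOR is not a listed objective, has no test or decision rule, and receives one descriptive sentence. Disease-specific outcomes are planned only for histologies with more than five participants. All of this stands.

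**Conclusion.** As written, 9.2.8 gives a late end date, or none, for one identifiable course: CR followed by one to four non-indicator skin lesions, with no new visceral site or qualifying edema. For a participant with that course, DOR is overstated relative to the rule in 9.1.5. The conclusion rests on the text and holds under either reference value for participants with 50 or fewer lesions.

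The size cannot be computed from the documents. The 0 to 16 weeks shown is an illustration at assumed growth rates, and nothing is known about how many participants would follow this course.

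The missing reference in 9.2.4 is a separate ambiguity: two analysts could assign different end dates to the same regrowth after PR. It is not an established overstatement. Apart from the small-count cases above, regrowth to baseline fails to end the response only if baseline is the reference.

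**What to change.** For the DOR analysis only:

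1. Reword 9.2.8 so that KS response duration ends at recurrence as defined in 9.2.5 or at progression, whichever is documented first.
2. State that, for DOR, percentage increases are taken from the smallest value recorded since treatment start, as 9.1.5 does.

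Leave the 9.2.4 progression criteria as they are. Section 4.7 uses them for treatment decisions, so the new wording should say that it applies to DOR alone. There is no need to change the size measure from diameters to products: that would be a preference, and it would reach beyond DOR.

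The cost is protocol and analysis-plan wording. KS is already assessed every 4 weeks, so no visits or measurements are added. Reported KS DOR may become shorter. Naming the nadir does not remove the small-count cases created by the five-lesion minimum; a sentence acknowledging them alongside the DOR summary is enough.

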9.3 Evaluation of Response for Participants with HIV-Associated Hodgkin Lymphoma

9.3.1 Definition of Response

The response definitions used for this study are the 2017 International Working Group Consensus RECIL 2017) [23]. This is similar to the Lugano criteria of 2014 where response is determined by a combination of Deauville score and CT scan criteria; however, only three lymph node targets are required in this evaluation criteria [23]. See table below.

9.3.2 Complete Response (CR)

- 1. Complete disappearance of all detectable clinical evidence of disease and disease-related symptoms if present before therapy.
- 2a. Typically FDG-avid lymphoma: In participants with no pretreatment PET scan or when the PET scan was positive before therapy, a post-treatment residual

- mass of any size is permitted as long as it is PET negative. PET negative is defined as a Deauville score of less than 4.
- 2b. Variably FDG-avid lymphomas/FDG-avidity unknown: In participants without a pretreatment PET scan, or if a pretreatment PET scan was negative, all lymph nodes and nodal masses must have regressed on CT to normal size (1.0 cm in their greatest transverse diameter for nodes > 1.5 cm before therapy). Previously involved nodes that were 1.1 to 1.5 cm in their long axis and more than 1.0 cm in their short axis before treatment must have decreased to 1.0 cm in their short axis after treatment.
- 3. The spleen and/or liver, if considered enlarged before therapy on the basis of a physical examination or CT scan, should not be palpable on physical examination and should be considered normal size by imaging studies, and nodules related to lymphoma should disappear. However, determination of splenic involvement is not always reliable because a spleen considered normal in size may still contain lymphoma, whereas an enlarged spleen may reflect variations in anatomy, blood volume, the use of hematopoietic growth factors, or causes other than lymphoma.
- 4. If the bone marrow was involved by lymphoma before treatment, the infiltrate must have cleared on repeat bone marrow biopsy. The biopsy sample on which this determination is made must be adequate (with a goal of > 20 mm unilateral core). If the sample is indeterminate by morphology, it should be negative by immunohistochemistry.

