9.3.3 Partial Response (PR) requires all of the following

- At least a less than or equal to a 30% decrease in sum of the product of the longest diameters (SLD) of up to three of the largest dominant nodes or nodal masses. These nodes or masses should be selected according to all of the following: they should be clearly measurable in at least two perpendicular dimensions; if possible, they should be from disparate regions of the body; and they should include mediastinal and retroperitoneal areas of disease whenever these sites are involved.
- 2. No increase should be observed in the size of other nodes, liver, or spleen.
- 3. Splenic and hepatic nodules must regress by 30% in their SLD or, for single nodules, in the greatest transverse diameter.
- 4. With the exception of splenic and hepatic nodules, involvement of other organs is usually assessable, and no measurable disease should be present.
- 5. Participants who achieve a CR by the above criteria, but who have persistent morphologic bone marrow involvement will be considered partial responders. When the bone marrow was involved before therapy and a clinical CR was achieved, but with no bone marrow assessment after treatment, participants should be considered partial responders.
- 6. No new sites of disease should be observed.
- 7. Typically FDG-avid lymphoma: for a participant with no pretreatment PET

scan or if the PET scan was positive before therapy, the post-treatment PET should be positive in at least one previously involved site.

8. Variably FDG-avid lymphomas/FDG-avidity unknown: if a pretreatment PET scan was negative, CT criteria should be used.

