9.3.4 Minor Response (MR)

Minor Response (MR) is defined as the following A participant is considered to have MR when he or she fails to attain the criteria needed for a CR or PR, less than or equal to 10% decrease or less than or equal to 20% increase in the sum of longest diameters of the target lesions. Typically FGD-avid lymphomas: the PET should be positive at prior sites of disease with no new areas of involvement on the post-treatment CT or PET.

9.3.5 Stable Disease (SD) is defined as the following A participant is considered to have SD when he or she fails to attain the criteria needed for a CR or PR, <10% decrease or less than or equal to 20% increase in the sum of longest diameters of target lesions. Typically FGD-avid lymphomas: the PET should be positive at prior sites of disease with no new areas of involvement on the post- treatment CT or PET.

Variably FDG-avid lymphomas/FDG-avidity unknown: if the pretreatment PET was negative, there must be no change in the size of the previous lesions on the post-treatment CT scan.

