% change from baseline	Complete disappear-ance of all target lesions and all nodes with long axis <10mm ≥30% decrease in the sum of longest diameters of target lesions (PR) with normaliza-tion of FDG-PET	≥30% decrease in the sum of longest diameters of lesions but not a CR	≥10% decrease in the sum of longest diameters of target lesions but not a PR (<30 %)	<10% decrease or ≤20% increase in the sum or the longest diameters of target lesions	>20% increase in the sum of longest diameters of target lesions For small lymph nodes measuring <15mm post-therapy, a minimum absolute increase of 5mm and the long diameter should exceed 15mm Appearance of a new lesion							
FDG-PET	Normalization of FDG-PET (Deauville score 1- 3)	Positive (Deauville score 4-5)	Any	Any	Any							
Bone marrow involvement	Not involved	Any	Any	Any	Any							
New lesions	No	No	No	No	Yes or No							

CR, complete response; CT, computerized tomography; FDG-PET, [18F]2-fluoro-2-deoxy-D-glucose; MR, minor response; PD, progression of disease; PR, partial response; SD, stable disease.

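### Section 9.3.2 allows a complete response with a PET-negative residual mass whatever its size, Table 6 asks for at least 30% shrinkage, and nothing says which decides the cHL response rate

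*Combined protocol and SAP*

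**What the plan says.** Section 9.3.1 names RECIL 2017 as the response standard for cHL and refers to the table below it. The criteria are then written out twice: as text in 9.3.2 to 9.3.5, and in Table 6.

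- **CR, text (9.3.2 item 2a).** For typically FDG-avid lymphoma with a positive or absent pretreatment PET, a residual "mass of any size is permitted as long as it is PET negative". No minimum shrinkage is set. Items 1, 3 and 4 (clinical disease and symptoms, spleen and liver, marrow) must also be met.
- **CR, Table 6.** Either the target lesions disappear, or there is a "≥30% decrease in the sum of longest diameters of target lesions (PR) with normaliza-tion of FDG-PET".
- **PR, text (9.3.3).** The size criterion reads "At least a less than or equal to a 30% decrease in sum of the product of the longest diameters (SLD". Item 7 adds that, in typically FDG-avid disease, "the post-treatment PET should be positive in at least one previously involved site". Table 6 asks for at least a 30% decrease with a positive PET.
- **MR, text (9.3.4).** "less than or equal to 10% decrease or less than or equal to 20% increase", and in typically FDG-avid disease "the PET should be positive at prior sites of disease". Table 6 instead has "≥10% decrease in the sum of longest diameters of target lesions but not a PR (<30"%), with any PET result.
- **SD, text (9.3.5).** "<10% decrease or less than or equal to 20% increase in the sum of longest diameters of target lesions", with the same positive-PET condition. Table 6 gives the same size range with any PET result.

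Section 10.4.1 reports the cHL response rate by RECIL with an exact binomial 95% interval, plus descriptive statistics for duration of response, and takes the criteria from Section 9.0 as a whole.

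**The concern.** Text and table use the same PET cut-off (Deauville below 4 in 9.3.2, scores 1 to 3 in Table 6), so a different reading of the PET cannot explain the gap. The difference lies in the shrinkage requirement. The same scans can make one participant a responder or a non-responder depending on which version the assessor opens.

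cHL objective response is a stated secondary objective (Section 1.2.2). With two versions in force, the choice could be made after the scans have been seen. It would change both the response rate and the set of participants who have a duration of response. PET-negative scans are expected in this cohort: Section 8.5.7 makes the week-49 scan depend on whether two consecutive negative scans have already been obtained.

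**Working it through.** **1. The plan's own interval.** Section 10.2 gives n = 12, ORR 70% and an exact 95% interval of 38% to 92%. The Clopper-Pearson limits are the 2.5% quantile of Beta(x, n − x + 1) and the 97.5% quantile of Beta(x + 1, n − x). With x = 0.70 × 12 = 8.4, they are 38.0% and 92.0%. The stated figure reproduces; its width is 92 − 38 = 54 points.

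**2. Which CR branch applies.** Section 8.1.7 requires a baseline PET/CT in this cohort. Item 2b of 9.3.2 covers only an absent or negative pretreatment PET, so item 2a is the branch for a participant who is PET positive at baseline. The protocol does not itself label cHL as typically FDG-avid, but no other item covers that participant.

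**3. PET negative after treatment, other CR items met.**

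| Change in sum of longest diameters | Text, 9.3.2 to 9.3.5 | Table 6 |
|---|---|---|
| decrease of 30% or more | CR | CR |
| 20% decrease | CR | MR |
| 5% decrease | CR | SD |

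Example: target diameters fall from 130 mm to 104 mm, a decrease of 1 − 104/130 = 20%, with Deauville 2. This is CR by the text and MR by the table. No other text category can take the case, because PR (item 7), MR and SD all require a positive post-treatment PET in typically FDG-avid disease. The conflict is confined to PET-negative participants with less than 30% shrinkage.

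**4. PET still positive, other conditions for the category met.** Here the 9.3.3 size criterion is read as a decrease of at least 30%.

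| Change in sum of longest diameters | Text | Table 6 |
|---|---|---|
| decrease of 30% or more | PR | PR |
| decrease of more than 10% but less than 30% | no category | MR |
| decrease of exactly 10% | MR | MR |
| decrease under 10%, or increase up to 20% | MR and SD both fit | SD |

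These differences change the table of response categories, not a CR plus PR rate.

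**5. Effect on the cHL rate.** Take objective response as CR plus PR, and suppose 8 of 12 respond by Table 6. The 8 is an illustration only. Each participant reclassified by the text adds 1/12 = 8.3 points; two add 2/12 = 16.7 points.

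| Responders | ORR | Exact 95% CI |
|---|---|---|
| 8/12 (Table 6) | 66.7% | 34.9% to 90.1% |
| 9/12 (one reclassified) | 75.0% | 42.8% to 94.5% |
| 10/12 (two reclassified) | 83.3% | 51.6% to 97.9% |

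**6. Is there a precedence rule?** Section 9.3.1 points to the table but does not say that it overrides the text following under the same heading. Section 10.4.1 points to Section 9.0, which contains both. By contrast, Section 5.1 states outright that it prevails over Appendix X where they differ. Section 9.3 has no such sentence.

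**The case against.** The best reply is that Section 9.3.1 names one external standard and points to Table 6, the only table in 9.3, and that 10.4.1 repeats RECIL; so Table 6 governs. That is a fair reading of intent, but it is a pointer and not a rule. Sections 9.3.2 to 9.3.5 are set out as working definitions under the same RECIL heading, and citing RECIL does not help when the protocol transcribes it in two incompatible ways.

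Several limits do stand:

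- Item 2a is one condition among several, so a residual mass alone does not make a CR.
- Section 10.4.1 does not say whether MR counts as an objective response. If it did, the 20% example would not move the ORR; only cases in the SD range or worse would, although the CR rate would still differ. CR plus PR is the protocol's own gloss in Section 2.2.1, but that passage is background on another study.
- The week-49 rule shows that negative scans are expected, not that negative scans with little shrinkage are.
- The PR wording has an evident meaning, supported by Table 6 and by the 30% regression asked of splenic and hepatic nodules in 9.3.3. The gap in the text for decreases between 10% and 30% exists only on that reading.
- Response is not the primary endpoint (Section 9.0), Section 10.2 calls the estimates preliminary, and 10.4.1 attaches no test or decision rule to the cHL rate.

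**Conclusion.** The concern holds. The text and Table 6 give different categories for a PET-negative participant with less than 30% shrinkage who meets the other CR items, and the plan does not say which applies. If cHL ORR is CR plus PR, each such participant is worth 8.3 points on a base of 12, against a planned interval 54 points wide. How many there will be cannot be known from the documents, and it may be none.

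The MR range in 9.3.4 is wrong as written, since it nearly repeats SD and contradicts Table 6, and the PR size criterion in 9.3.3 cannot be applied literally. The threshold for progression, an increase of more than 20%, agrees between text and table. The documents alone cannot show which transcription is faithful to RECIL 2017, so the conclusion is that they must be reconciled, not that either one is correct.

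**What to change.** Check both versions against the cited RECIL 2017 criteria and amend Section 9.3 so that one set of thresholds remains:

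1. Settle the PET-negative CR rule: either any residual size, or a stated minimum decrease.
2. Correct the MR range in 9.3.4 so that it is distinct from SD, and align the PET conditions for MR and SD between text and table.
3. Restate the PR size criterion in 9.3.3 in plain terms, including whether the measure is a sum of diameters or of products.
4. State in 9.3.1 or 10.4.1 which version governs if any difference remains, and that cHL ORR is CR plus PR.

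Make the change before cHL response is summarised, and re-check any cHL responses already classified. The cost is amendment wording and a review of at most 12 participants; no new data or visits are needed.
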